**Efficacy of Tranexamic Acid in preventing post operative
blood loss and associated complications in bone
sarcoma patients treated with limb salvage surgery: A
randomized controlled trial.**

IRB# IRB-22-07

DATE OF DOCUMENT: 06-04-2022

STUDY PROTOCOL

Efficacy of Tranexamic Acid in preventing post operative blood loss and associated complications in bone sarcoma patients treated with limb salvage surgery: A randomized controlled trial.

Introduction:

Limb salvage surgery for malignant bone tumors results in extensive bone and soft tissue resection which leads to massive bleeding and requiring a large number of transfusions [1] [2]. Blood transfusions have their own complications like hemolytic reaction, graft versus host disease, the spread of infection and sometime can lead to mortality [3]. Blood loss and related complications may lead to high risk of reoperation, an increased hospital stay, and increases burden over the health resources especially among anemic cancer patients [4].

Tranexamic acid (TXA) is a synthetic analog of lysine that prevents fibrinolysis by blocking the lysine binding sites on plasminogen and it has been extensively used over the past decade in orthopedic surgeries to decrease perioperative blood loss and the transfusion rate [5][6]. Perioperative use of TXA has been shown to reduce intraoperative and postoperative blood loss and to decrease transfusion rates in both total knee arthroplasty and total hip arthroplasty [7][8]. Furthermore, it results in higher postoperative hemoglobin, decreased postoperative pain, swelling, length of hospital stays, and higher patient satisfaction [9][10].

Although there is a long-standing concern about TXA-induced hypercoagulability that may increase the risk for postoperative venous thromboembolism (VTE), there are multiple studies even in high-risk patients supporting its safe use [3][11]. In a review of more than 1,000 patients, 240 of which had multiple risk factors for embolic disease including known prothrombotic conditions, those who received TXA had no additional thrombotic events [12]. In addition, two studies have documented an overall reduction in healthcare costs due to fewer transfusions.[11][13].

Despite ample research documenting the safety and efficacy of perioperative TXA in patients undergoing arthroplasty, there is no known clinical trial focusing on TXA's use in musculoskeletal oncology patients undergoing endoprosthesis reconstruction. Nonetheless, TXA is used within the musculoskeletal oncology community, with its use varying from surgeon to surgeon. Surgeons who use TXA do so with the intent of limiting perioperative blood loss and transfusion rates in these high blood-loss procedures. However, without clinical trial to support its use in this cohort, these patients, who tend to have an increased number of comorbidities, could be inheriting an increased risk of perioperative complication without the benefits documented. Conversely, patients within this cohort that do not receive TXA could be missing out on the clinical benefits of TXA seen in patients undergoing arthroplasty. This randomized clinical trial will determine the efficacy of tranexamic acid in musculoskeletal oncology population who underwent wide local excision and reconstruction with endoprosthesis and will result in the formation of a guideline about its efficacy in reducing blood loss and adverse events that can be resulted by the use of tranexamic acid in the musculoskeletal oncology population.

Objectives:

To determine the efficacy of tranexamic acid in musculoskeletal tumor who underwent wide local excision and reconstruction with endoprosthesis and determine adverse events that can be resulted by the use of tranexamic acid.

Primary outcome measures:

Blood loss in a surgical patient can be monitored by:

- Drop-in hemoglobin in 72 hours
- The number of transfused PRBC unit
- 72-hour total blood loss as calculated by hemoglobin balance method

Hemoglobin balance method:

The Hemoglobin - balance method is based on the balance of Hemoglobin during the perioperative period of surgery. It is regarded as an important method with intuitive expressiveness and high accuracy and often addresses contemporary clinical issues [14]

$Hb_{\text{loss total}} = BV \times (Hb_i - Hb_e) \times 0.001 + Hb_t$	$Hb_{\text{loss total}}$ (g): The loss volume of Hb
$V_{\text{loss total}} = 1000 \times Hb_{\text{loss total}} / Hb_i$	Hb_i (g/L): The Hb value before surgery
Generally, 1 U banked blood is considered to contain 52 ± 5.4 g Hb[5]	Hb_e (g/L): The Hb value after surgery;
	Hb_t (g): The total volume of blood transfusion

Secondary outcome measures:

- Thromboembolic events: to be observed over six weeks from the date of surgery
- Hospital stay
- drain output till 72 hours

Methodology

Study Design: A Randomized control trial (RCT)

Setting: Department of surgical oncology, Shaukat Khanum Memorial Cancer Hospital and Research Center, Lahore.

Sample size:

Sample size was calculated on the basis of previous study published by Haase, Douglas R. in 2020. Mean post-operative blood loss in TXA group and non TXA were 981 ± 290 mL and 1542 ± 394 mL, respectively. [02] At 80% power, 95% confidence interval, assuming 10% drop out rate, a total of 36 patients included in this study divided into two groups (18 in each group, TXA versus non TXA) would be required in this study.

Sample selection:**Inclusion criteria:**

Patients with primary or metastatic bone tumors who underwent a resection and an endo-prosthetic reconstruction of the proximal femur, distal femur, proximal tibia and proximal humerus. All patients will be tested for liver function using PT (INR), renal function by serum creatinine and Marrow function by CBC

Exclusion Criteria:

- Patient with a congenital or acquired coagulopathy
- Severe renal or liver insufficiency
- Previous thromboembolic condition
- A patient who received perioperative plasma product
- Pelvic tumor
- Patient who is taking anti-coagulant before surgery
- Patient allergic to tranexamic acid

Enrollment duration: Being a dedicated cancer center, a large number (30-40 per year) of Limb salvage surgeries are performed at Shaukat Khanum Memorial Cancer Hospital. The above-given sample size can therefore be achieved in 10 months.

Dose of tranexamic Acid: A single dose of tranexamic acid will be given intravenously at time of induction according to body weight i.e., 15 mg/kg

Anti-coagulation Protocol: All limb salvage patients started on anticoagulant Injection Enoxaprin subcutaneously after 24 hours of surgery according to body weight i.e. 1.5 mg/kg. Enoxaprin converted to oral tablet Aspirin 75 mg on discharge for 4 weeks.

Study Duration: 12 months after the start of enrollment.

In house admission: Limb salvage surgery patients remain admitted on the floor for an average of 5 days

Follow up Schedule: Physical follow up in clinic 2 weeks after surgery (as per institutional guidelines) and a second follow up at 4 weeks after surgery

Randomization: Intraoperative randomization, patients would be allocated to either of the groups by selecting names from sealed envelopes.

Type of randomization: Computerized block randomization. This will ensure a similar number of patients in both groups. Patients will have their names written on an envelope with contents of the envelope indicating whether tranexamic acid should be given or not. Only one member of research team will be aware of the contents of the envelope, who will not be present in Operation Theater at the time of surgery and will not take part in data collection. Patient in control group will be given 10 cc of normal saline as as placebo.

Blinding: It will be a triple-blind trial since the patients will be unaware of the group to which they have been randomized. The statistician carrying out data analysis and examiners/interviewers carrying out clinical examinations/interviewing patients will also be unaware of the status of tranexamic acid.

Minimizing Bias: It is not possible to eliminate bias altogether. However, the performance bias of the operating surgeon will be limited by not revealing the contents of the sealed envelope. The interviewer's bias will be limited by ensuring that the interviewer is not aware of tranexamic acid status at the time of the interview and by ensuring a standardized interaction between the patient and interviewer.

Intervention: Surgeon who will carry out Limb salvage surgeries, will be a consultant with > 5-year experience in Limb salvage. A single standardized technique will be used in all of the patients.

There is a difference of opinion about the use of tranexamic acid in surgeons at SKMH and both surgical options are practiced. The trial will therefore pose no additional risks to the patients.

References

- Wei W, Wei B: Comparison of topical and intravenous tranexamic acid on blood loss and transfusion rates in total hip arthroplasty. J Arthroplasty 2014;29:2113-2116

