- Femur _____
- Tibia _____
- Other

Group:

- Tranexamic Acid Given
- Tranexamic Acid Not Given

Length of Bone Resected _____ **Cm**

Wound Healing: (Satisfactory / Unsatisfactory)

Preoperative Hemoglobin _____gms

Preoperative INR _____

Intraoperative Blood Loss: _____mls

Postoperative Hemoglobin after 24 Hours _____gms

Postoperative Hemoglobin after 72 Hours _____

Number of PRBC Transfused Within 72 Hours of Surgery _____

Blood Loss Calculated By Direct Hemoglobin Method _____

Drain Output in 72 Hours: _____mls

Any Thromboembolic Event: _____

Status of Ambulation:

STATISTICAL ANALYSIS PLAN:

Statistician independently pooled data from each case then conducted statistical analysis using SPSS Descriptive data are presented as mean \pm standard deviation (*SD*). Odds ratio (*OR*) with 95% confidence intervals (*CI*) or mean differences (*MD*) with 95% *CI* were calculated for dichotomous and continuous outcomes, respectively. Numerical and measured data were compared using a *t*-test and χ^2 -test, respectively. An appropriate power and sample size calculator was used to calculate statistical power. The following parameters were used in the calculations: α , probability of a type I error for a two-sided test; P_0 , probability of exposure in controls; N , number of patients; m : ratio of control to experimental subjects; and Ψ , odds ratio of exposure in experimental subjects relative to controls. $P < 0.05$ was considered significant.

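### The promised guideline on adverse events cannot rest on 18 TXA patients: zero thromboembolic events would still be compatible with a risk of up to 18.5%, and the planned odds ratio and chi-square test do not suit such counts

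*Combined protocol and SAP*

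**What the plan says.** - **Purpose.** The last paragraph of the Introduction says that this trial of TXA in the musculoskeletal oncology population "will result in the formation of a guideline about its efficacy in reducing blood loss and adverse events that can be resulted by the use". The Objectives also include determining TXA's adverse events.
- **Open risk.** The same paragraph says that, without a trial, these patients "could be inheriting an increased risk of perioperative complication without the benefits documented". Its next sentence adds that untreated patients may be forgoing a benefit.
- **Size.** The Sample size section takes mean blood loss from one previous study (981 ± 290 mL with TXA, 1542 ± 394 mL without). "At 80% power, 95% confidence interval, assuming 10% drop out rate", it arrives at 36 patients: "18 in each group, TXA versus non TXA".
- **Safety outcome.** Thromboembolic events over six weeks are a secondary outcome. No expected rate, margin or precision target is given.
- **Population.** The Exclusion Criteria include "Previous thromboembolic condition", coagulopathy, and anticoagulant use before surgery.
- **Analysis.** The Statistical Analysis Plan gives odds ratios with 95% confidence intervals for dichotomous outcomes, names the t-test and chi-square test, defines alpha as the "probability of a type I error for a two-sided test", and uses P < 0.05. It has no rule for arms without events.
- **Risk of taking part.** The Intervention section notes that local surgeons differ on TXA and that both options are in use, and concludes: "The trial will therefore pose no additional risks to the patients".

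**The concern.** A guideline statement on adverse events needs either a reasonably tight upper limit on the risk or a comparison able to detect a relevant rise. The number of patients was set for neither. If events are uncommon, the likeliest safety result is few or none in each arm. The planned odds ratio then cannot be computed, and the significance of a small imbalance depends on which test is used.

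At stake is the safety conclusion carried forward from the trial. Data compatible with a wide range of risks could end up supporting a guideline statement for a broader population than the one enrolled.

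**Working it through.** **Inputs.** 18 per arm, 10% dropout and the blood-loss means and SDs come from Sample size. The two-sided test and the 0.05 threshold come from the Statistical Analysis Plan. The documents give no thromboembolic event rate for this population, so the rates of 5%, 10% and 20% below are assumptions.

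**1. The plan's own figure.** Difference = 1542 − 981 = 561 mL. Pooled SD = √((290² + 394²)/2) = 345.9 mL. Normal approximation: n = 2 × (1.960 + 0.842)² × 345.9² / 561² ≈ 6 per arm, and 6/0.9 gives 7 per arm (14 in total). The exact t calculation gives 8 per arm, and 8/0.9 gives 9 per arm (18 in total). The stated 36 is not reproduced. That is a separate matter. What counts here is that 18 per arm gives over 99% power for blood loss on these inputs, so the shortfall concerns safety only.

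**2. Upper limit after no events.** The exact (Clopper-Pearson) two-sided 95% upper limit for 0/n is 1 − 0.025^(1/n).
- n = 18: 1 − 0.8147 = 18.5%.
- n = 16 (18 × 0.9 = 16.2): 1 − 0.7941 = 20.6%.
- One-sided 95%, n = 18: 1 − 0.05^(1/18) = 15.3%.

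These bound the absolute risk in the TXA arm, not the excess over control.

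**3. How often no event would be seen in 18 TXA patients.** True risk 5%: 0.95^18 = 0.397, about 40%. True risk 10%: 0.90^18 = 0.150, about 15%.

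**4. Odds ratio.** With a events on TXA and b on control, OR = a(18 − b) / [b(18 − a)]. If b = 0 and a > 0 it is infinite. If a = 0 and b > 0 it is zero, with no finite log odds ratio and so no standard interval. If both are zero it is 0/0.

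**5. Test, for 4/18 against 0/18.** Each event cell has an expected count of 4 × 18/36 = 2.
- Chi-square, uncorrected: 36 × (4×18 − 14×0)² / (18 × 18 × 4 × 32) = 4.50, P = 0.034.
- Chi-square, continuity-corrected: 36 × (72 − 18)² / 41,472 = 2.53, P = 0.112.
- Fisher, two-sided: 2 × C(18,4)/C(36,4) = 2 × 3,060/58,905 = 0.104.

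The same data fall on either side of 0.05, and the plan does not say whether a correction applies.

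**6. Power at 18 per arm.** This sums the binomial probabilities of all pairs of event counts that give P < 0.05.

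| Assumed risks, control v TXA | Chi-square, uncorrected | Chi-square, corrected | Fisher |
|---|---|---|---|
| 5% v 20% | 25% | 7% | 13% |
| 5% v 10% | 4% | 0.3% | 1% |

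The conclusion is the same under every choice.

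**The case against.** Sizing a trial on a primary outcome and carrying safety as a secondary one is ordinary design, and no trial of 36 patients could establish the safety of TXA. The plan also does intend to collect and report events: thromboembolism is a named outcome with a proforma field, and intervals are planned. All of that stands. It means no larger trial is being asked for. It does not rescue a promise of an adverse-event guideline, nor an odds ratio that fails in a likely scenario.

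Four stronger readings are tempting, and the documents do not support them.
- **The plan contradicts itself on risk.** A reader might set "The trial will therefore pose no additional risks to the patients" against "could be inheriting an increased risk of perioperative complication without the benefits documented". The Intervention sentence follows from both options being in local use and reads fairly as no risk beyond current practice. The Introduction describes equipoise. An open drug risk and no added risk from taking part can both hold. The 18.5% limit does not refute the Intervention sentence, which is only loosely worded.
- **A null result will be declared safe.** Nothing in the plan says so. It only lacks a statement ruling this out.
- **The excluded patients are those who motivate the trial.** The Introduction speaks of comorbidities in general. The proforma records hypertension, diabetes and ischaemic heart disease, and metastatic disease is eligible. The exclusions limit generalisability and do no more than that.
- **The holder of the allocation should tally events by arm.** The section on type of randomization keeps that person out of data collection, so such a tally would conflict with the plan.

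**Conclusion.** The point holds as a mismatch between the stated safety conclusion and what the design can deliver. After no events in 18 TXA patients, an absolute risk of up to 18.5% stays compatible with the data (two-sided exact 95% limit). Power to detect even a rise from an assumed 5% to 20% is about 25% by uncorrected chi-square and 13% by Fisher. The planned odds ratio and chi-square test are poorly suited to such sparse counts.

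The 18.5% assumes that all 18 are evaluable and that events are fully ascertained over six weeks. The last listed visit is at 4 weeks, so the observation window and the visit schedule must be reconciled. The power figures depend on assumed rates. The efficacy analysis does not depend on any of this. The correction is worth making because it costs almost nothing.

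**What to change.** 1. **Introduction, last paragraph.** Limit the guideline claim to efficacy in reducing blood loss, and state that the safety results are descriptive.
2. **Statistical Analysis Plan.** Add wording such as: *Thromboembolic events will be reported as counts with exact (Clopper-Pearson) 95% limits in each arm. If the arms are compared, an exact test will be used. A non-significant difference will not be reported as evidence of safety. The safety conclusion applies to patients without previous thromboembolism, coagulopathy or anticoagulant use before surgery.*
3. **Intervention.** Reword the no-additional-risks sentence to say that taking part poses no risk beyond current local practice, and that the complication risk of TXA in this population is still open, as the Introduction says.

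The cost is three changes of wording, with no extra patients, visits or staff. The downside is a weaker stated safety claim.

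### The objective promises adverse events of tranexamic acid, but thromboembolism is the only adverse-event outcome, and death, reoperation, transfusion reaction, infection and drug reaction have no dedicated field

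*Combined protocol and SAP*

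**What the plan says.** The title concerns "blood loss and associated complications in bone" sarcoma patients. The Objectives section pairs efficacy with a second aim, to "determine adverse events that can be resulted by the use of tranexamic acid". The Introduction closes by expecting the trial to lead to a guideline on both efficacy and adverse events.

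The Introduction also describes the harms of bleeding and transfusion: "Blood transfusions have their own complications like hemolytic reaction, graft versus host disease, the spread of infection and sometime can lead to mortality", and "Blood loss and related complications may lead to high risk of reoperation, an increased hospital stay".

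Three secondary outcomes are listed. One is an adverse event: "Thromboembolic events: to be observed over six weeks from the date of surgery". The others are "Hospital stay" and drain output to 72 hours. The Follow up Schedule has clinic visits at 2 and 4 weeks.

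The Proforma has a free-text line headed "Any Thromboembolic Event", an item "Wound Healing: (Satisfactory / Unsatisfactory", a count of PRBC units within 72 hours, and ambulation status. The Statistical Analysis Plan gives general methods for dichotomous and continuous outcomes and does not mention adverse events.

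**The concern.** Safety is half of the stated objective, yet it rests on one outcome. If an event has no outcome, no field and no analysis, nothing in the plan brings it into the data by arm. A return to theatre on day 4, for example, falls outside the 72-hour blood-loss and transfusion fields and has no line of its own.

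Death also affects the one safety outcome that is listed. A patient who dies cannot afterwards be observed to have a thromboembolism. Without a vital-status field, the form cannot separate a death with no diagnosed clot from survival without an event. Such facts may be hard to recover reliably once the trial has ended and allocation is known.

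**Working it through.** No figure in the plan bears directly on this point, so the main check sets the stated aims against what is collected.

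| Event | Where the protocol raises it | Listed outcome | Proforma field |
|---|---|---|---|
| Thromboembolism | Introduction, as a drug risk | Yes, six weeks | Yes, free text, undated |
| Longer hospital stay | Introduction, from blood loss | Yes | None |
| Reoperation | Introduction, from blood loss | No | None |
| Haemolytic reaction | Introduction, from transfusion | No | None |
| Graft versus host disease | Introduction, from transfusion | No | None |
| Infection | Introduction, from transfusion | No | None dedicated; an unsatisfactory wound may partly reflect wound infection |
| Death | Introduction, from transfusion | No | None |
| Reaction to tranexamic acid | Exclusion Criteria (allergy) | No | None |

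Of the six consequences of transfusion or blood loss named in the Introduction (haemolytic reaction, graft versus host disease, infection, death, reoperation, longer stay), one is an outcome. That one, hospital stay, has no field on the Proforma.

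**What added safety counts could show.** Take n = 18 per arm as stated under Sample size; whether that number follows from its inputs is a separate question. The plan's 10% dropout gives 18 × 0.9 = 16.2, so about 16 evaluable.

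- Zero events in an arm: the one-sided 95% upper bound is 1 − 0.05^(1/n). For n = 18 this is 1 − 0.05^(1/18) = 15.3%. For n = 16 it is 17.1%.
- Chance of at least one event in an arm of 18: 1 − (1 − p)^18. The documents give no event rates, so p is assumed. For p = 1%, 2%, 5% and 10% the results are 17%, 30%, 60% and 85%.
- Power to separate assumed rates of 5% and 20%, two-sided α = 0.05, normal approximation. The pooled rate is 0.125. The null standard error is √(2 × 0.125 × 0.875 / 18) = 0.110, and the alternative standard error is √((0.05 × 0.95 + 0.20 × 0.80) / 18) = 0.107. Power = Φ((0.15 − 1.96 × 0.110) / 0.107), about 27%.

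The counts would therefore be descriptive. That limits how they are analysed; it does not remove the reason to collect them.

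**The observation window.** Thromboembolism is to be observed for six weeks, but the last planned visit is at 4 weeks. Any item tied to six weeks has no scheduled contact at its end, and the two passages must be reconciled.

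**The case against.** The strongest reply separates harms of the drug from harms of bleeding and transfusion. The objective concerns adverse events of tranexamic acid. The only drug harm the Introduction discusses is hypercoagulability and venous thromboembolism, which is the event the trial lists. The complications of transfusion and blood loss are background, and the allergy exclusion is an eligibility rule that promises no outcome. Much of this stands: the Introduction's list should not be read as a list of tranexamic acid adverse events. But the objective is not worded as thromboembolism alone, and the title's reference to associated complications, though undefined, does reach the bleeding-related harms.

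A reader might go further in three ways that the documents do not support.

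- *Only thromboembolism is collected.* Wound healing and ambulation status are on the Proforma, and hospital stay is a listed outcome. Thromboembolism is the only adverse-event outcome, which is a narrower statement.
- *A death before six weeks is scored as no event.* No scoring rule exists. A blank free-text line could be read as missing, a death could be counted as dropout, and a recognised fatal clot would fit the existing line. The handling of death is unspecified.
- *One missed event biases an arm by 1/18 = 5.6%.* That is only the share of an arm that one patient represents. It estimates no bias.

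It may also be said that hospital systems would pick up serious events. The documents describe no route from those systems into the trial data or analysis.

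**Conclusion.** The concern holds in limited form. The plan states a general adverse-event objective and a title that covers complications, and supports them with one adverse-event outcome. Death, return to theatre, transfusion reaction, diagnosed infection and suspected drug reaction have no outcome, no dedicated Proforma field and no analysis text. Followed as written, the trial cannot report them by arm, and the status of a patient who dies without a diagnosed clot is ambiguous on the form.

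The size of the gap is a matter of coverage: one of six named complications of transfusion or blood loss is an outcome. No numerical bias can be derived, because the documents give no event rates. The primary blood-loss comparison and the sample size are untouched. The conclusion assumes that the Proforma shown is the only data form, since the documents describe no other. The change should be made because it is cheap and bears directly on a stated objective.

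**What to change.** Add dated yes/no items to the Proforma, and list them as secondary outcomes: death (with cause), return to theatre (with reason), transfusion reaction, infection, and suspected reaction to study drug. Tie the wound-healing item to one planned visit, at 2 or 4 weeks, state what counts as unsatisfactory, and list it as a secondary outcome.

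State the window. Either collect the items from the ward record and the planned visits through 4 weeks, or, if six weeks is kept, add a record check or phone call at six weeks. In either case, reconcile the six-week thromboembolism window with the visit schedule.

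In the Statistical Analysis Plan, specify descriptive counts per arm with no formal safety test, and show deaths separately from patients alive and event-free.

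The cost is a slightly longer form, a few more table rows and possibly one brief status check per patient at six weeks. If the items are not added, narrow the title and objective to thromboembolism. That removes the mismatch but gives up the wider safety question that the Introduction uses to motivate the trial.

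### Three unranked primary outcomes are each tested at P < 0.05 with no success rule or multiplicity control; blood loss is implied as the lead outcome but never declared

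*Combined protocol and SAP*

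**What the plan says.** The protocol's Primary outcome measures section opens with "Blood loss in a surgical patient can be monitored by" and lists three items: "Drop-in hemoglobin in 72 hours", "The number of transfused PRBC unit" and "72-hour total blood loss as calculated by hemoglobin balance method". No item is ranked. The section does not say whether one significant result is enough or all three are needed.

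The haemoglobin-balance formula follows. Haemoglobin lost equals blood volume times the haemoglobin fall, plus transfused haemoglobin, and the result is converted to a volume using the preoperative value. For the transfusion term, "1 U banked blood is considered to contain" 52 ± 5.4 g of haemoglobin.

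The Sample size section rests on one quantity: "Mean post-operative blood loss in TXA group and non TXA were" 981 ± 290 mL and 1542 ± 394 mL. It does not call this the deciding outcome or tie it to the 72-hour haemoglobin-balance measure.

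The Statistical Analysis Plan gives generic t-tests and chi-square tests, a two-sided alpha and one threshold, P < 0.05. It names no primary outcome, order of testing, alpha split or adjustment. Its listed power parameters (exposure probability in controls, odds ratio) describe a binary comparison and match none of the three outcomes.

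**The concern.** The false-positive rate and the power of this trial both depend on a success rule that has not been written. Under an any-one rule, three chances at 0.05 give more than a 5% risk of a false finding. Under an all-three rule that risk falls, but a real effect can be missed.

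The three outcomes are also not interchangeable. The third is calculated from the other two. A transfused unit raises the postoperative haemoglobin and so reduces the raw drop, while the formula adds that unit back. One set of data can therefore show a clear difference in calculated blood loss and little difference in haemoglobin drop.

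With no rule on paper, the choice of what counts can be made after the results are known. That matters because the Introduction says the trial "will result in the formation of a guideline about its efficacy in reducing blood loss".

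**Working it through.** **1. The plan's own figure.** Inputs from the Sample size section: difference 1542 − 981 = 561 mL; SDs 290 and 394; 80% power; two-sided 0.05; 10% dropout.
- Pooled SD = √[(290² + 394²)/2] = 345.9 mL; d = 561/345.9 = 1.62.
- Normal approximation: n = 2(1.96 + 0.84)²/1.62² ≈ 6 per arm; 6/0.9 rounds up to 7, or 14 in total. The noncentral t gives 8 per arm, 18 in total.
- The stated 36 is not reproduced. It exceeds what these inputs need, which is a separate matter and does not weaken the fix below.

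**2. Any-one rule: bounds.**
- Ceiling: 3 × 0.05 = 15% two-sided; 3 × 0.025 = 7.5% for a false claim of benefit.
- Independent outcomes: 1 − 0.95³ = 14.3%; benefit only, 1 − 0.975³ = 7.3%.

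**3. Any-one rule: correlated outcomes.** The outcomes share components, so independence is not the right model. Two checks were made at 16 per arm (18 × 0.9 = 16.2).
- Three equally correlated normal outcomes (40,000 replicates): 12.5%, 9.9%, 8.3% and 7.4% at correlations of 0.5, 0.8, 0.9 and 0.95. The correlations are assumed.
- Outcomes built from the protocol's formula with no treatment effect. Both arms had a mean loss of 981, 1262 or 1542 mL, with 52 g per unit. Assumed: blood volume 4500 (SD 600) mL, preoperative Hb 115 (SD 12) g/L, and 16 transfusion rules (four patterns at 70, 80, 90 and 100 g/L). The rules are modelling assumptions, not recommendations. Three t-tests gave 8.2% to 12.8% two-sided and 4.0% to 7.1% for false benefit. Repeat runs gave 7.6% to 13.2% and 3.5% to 7.6%. Rounded: about 8% to 13%, and about 4% to 7.5%.

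**4. All-three rule.** When all three outcomes are null, the formula-based runs gave at most about 0.2%. The equal-correlation runs gave 0.3% at correlation 0.5 and 2.9% at 0.95. If only one outcome is null, the error is bounded by that test's own 5%. Type I error therefore does not inflate.

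**5. Why all three could fail to agree.** From the formula, BV × (Hb_i − Hb_e) × 0.001 = Hb_loss − Hb_t, and Hb_loss = V_loss × Hb_i/1000. The arms have the same mean raw drop (at equal blood volume) when the difference in transfused haemoglobin equals the difference in haemoglobin lost. For 561 mL at 52 g per unit:

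| Assumed preoperative Hb (g/L) | Haemoglobin (g) | Extra units per control patient |
|---|---|---|
| 100 | 56.1 | 1.08 |
| 115 | 64.5 | 1.24 |
| 130 | 72.9 | 1.40 |

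So 1.1 to 1.4 extra units per control patient would cancel the haemoglobin-drop difference. The documents do not give the transfusion practice needed to say how often that happens.

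**6. Power if blood loss is the primary.** Noncentral t, d = 1.62, 16 per arm: 99.3% at 0.05 and 97.5% at 0.0167 (= 0.05/3). The difference detectable with 80% power is 354 mL at 0.05 and 416 mL at 0.0167.

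**The case against.** The strongest reply is that the plan already has a lead outcome. The title is about blood loss, the three items are introduced as ways of monitoring it, a formula is given for that measure alone, and the only sample-size calculation uses a blood-loss volume. This stands as evidence of intent, and it is wrong to read the plan as having no lead outcome at all. But an implied outcome is not a prespecified one. The sample-size quantity is not tied to the 72-hour calculated loss, and the Proforma also collects intraoperative loss and drain output.

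A second reply is that, at the plan's assumed effect, an any-one rule would hardly change the decision, since blood loss alone would be significant in about 99% of trials. This also stands. The harm lies where the effect is null or much smaller than 561 mL, or where an all-three rule is adopted. The documents do not propose an all-three rule.

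A reader might infer that the trial's false-positive rate is 14.3%, or that transfusion will probably mask the haemoglobin drop. The documents support neither. The outcomes are correlated, so 14.3% is what independence would give. Blood volume, baseline haemoglobin and transfusion practice are not given, so the power of haemoglobin drop, of PRBC units, and of all three together cannot be stated.

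**Conclusion.** The point holds. There are three unranked primary outcomes, one threshold for each test, and no success rule or adjustment. This is more than missing detail, because following the plan as written would let an inflated or after-the-fact claim stand.

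The sizes differ in what supports them. The 15% ceiling needs only three tests at 0.05. The ranges of about 8% to 13% for any false positive and about 4% to 7.5% for false benefit rest on assumed transfusion rules, blood volume and baseline haemoglobin; inflation above 5% appeared at every setting tried. The 0.2% for an all-three rule applies only when all three outcomes are null and should not be read as the general error rate of such a rule. Masking of the haemoglobin drop is possible by the protocol's own formula, but its frequency is unknown.

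**What to change.** Before any look at outcome data by arm, add a dated statement to the protocol and the SAP to this effect: the single primary outcome is total blood loss to 72 hours by haemoglobin balance, tested at two-sided 0.05; haemoglobin drop and PRBC units are secondary, reported with 95% confidence intervals and without a confirmatory claim.

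An acceptable alternative is to keep three primaries under Holm, or under Bonferroni at 0.0167 each. Blood loss would keep at least 97.5% power, but power for the other two cannot be checked from the documents.

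The SAP is written in the past tense, which does not settle whether data by arm have been seen. If they have, report all three outcomes and disclose that the primary was chosen late.

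The cost is wording only, with no extra patients. The downside is that only one outcome carries the confirmatory claim; little information is lost, because the other two are inputs to it. The 99.3% power holds provided that the blood loss used for the sample size behaves like the 72-hour haemoglobin-balance measure.

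Three supporting clarifications are separate from this point: state how blood volume is calculated, record the inputs for it on the Proforma, and reconcile the Proforma label "Blood Loss Calculated By Direct Hemoglobin Method" with the method named in the protocol.
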